### **Power Calculation**

The study design is targeted to achieve 80% power before October of 2017. Given our 0.048 alpha level for our final analysis, and controls anticipated to have a 13.52% readmission rate based on estimates, this requires approximately 320 patients enrolled per month (n = 2234). We assessed the feasibility of this target after observing there were approximately 508 eligible patients per month based on medical center data collected from 10/1/2015 - 9/30/2016. We noted approximately 11% of these patient would need to be

excluded after randomization due to mis-categorized hospital discharge status affecting study eligibility reducing potential monthly enrollment to 452 (n = 3164, or 1582 patients per arm). In **Table 1**, we

**Table 1 - Power and Sample Size Scenarios** 

	Conse	rvative	Ambitious	
Control Group Readmission Rate†	13.52%	13.52%	13.52%	13.52%
Intervention Group Readmission Rate	9.60%	9.10%	10.20%	9.70%
Power	80%	90%	80%	90%
Detectable Difference	3.9%	4.4%	3.3%	3.8%
Projected Study Sample Size	1117	1117	1582	1582

\*2 group X^2 test of equal proportions (equal n's), 2-sided text, final analysis  $\alpha$  = 0.048

illustrate conservative and ambitious enrollment scenarios with estimates for 80% and 90% power. Considering we have 1 Phone Call Study Nurse and will miss enrollment days for paid time off or sick days, we opted for a more conservative power target and detectable differences of 80% and 3.9% respectively. This carries an associated enrollment of 1117 patent per arm (n = 2234, or 11 patients per day).

#### POTENTIAL RISKS AND BENEFITS

We anticipate minimal risk to patient as none will receive less than what was the VUMC standard discharge practice (no structured follow-up call) prior to the initiation of the phone call program in 2016. In addition, there are no invasive tests or sensitive questions. The phone call nurse currently is able to attempt calls for 75% of all discharged inpatient general medicine patients. She successfully reaches 30% after an average of 2.1 call attempts. With study call efforts focused on the intervention arm we anticipate she will attempt a call for all patients assigned to the Phone Call Group, and complete up to 3 call attempts. This may improve the intervention delivery rate. Patients that may have received a call before the study will not be exposed to potential benefits from the follow-up phone call. This, however, is anticipated to balance with the patients in the intervention arm that would otherwise have not been exposed to a call. Despite mixed results on the effectiveness of a discharge phone call program reported in the literature, we expect to observe a benefit from exposure to the phone call intervention,  particularly in those found to require discharge plan implementation assistance. Other risks are related to potential breaches in confidentiality in the handling of patient protected health information (PHI). To avoid this, all PHI will be transferred among key study personnel and stored using REDCap. To avoid breaches in confidentiality induced by the Study Phone Call Nurse potentially sharing PHI with a friend, family member or stranger answering the patient's phone, she requests identifying information before initiating a discussion of the patient discharge care plan. Health proxies, caretakers or family members

 ${}^{\dagger}\, Historical\, VUMC\, readmission\, rates$ 

may be spoken to with the explicit verbal permission of the patient. This is the current standard of medical care for follow-up phone call health service and not specifically implemented for the purpose of this study.

#### SIGNIFICANCE AND IMPACT

The results of the primary endpoint analysis of this study will inform an evidence-based VUMC decision on whether to invest in a hospital discharge follow-up phone call program for medical patients across the enterprise. If launched, our secondary outcome analyses results will inform the design of the program to maximize patient benefit. We intend to publish our result in the medical literature to contribute to knowledge on the efficacy of post-hospital discharge follow-up phone calls as a means of delaying hospital readmissions, improving patient's transition from inpatient to outpatient care, and improving patient satisfaction.

### APPENDIX I - Follow Up Phone Call Data Collection Form (Phone Call Starform)

Provider (indexing):	[name]	** This will change the provid	er displayed	in the all documents listing of S	tarPanel. ***)
*Standard	`		1 7		Ź
Document Name:	Clinical Communi	cation		Discharge Follow-up	
Comment for Indexin	g (optional):	▼			
VANDERBILT UNIV POST DISCHARGE					
Date of Discharge:	2/12/2015				
Patient Home [contact]				
CALL INFO:					
Call Attempt Date ar	nd Time:	Pt Location:		Call Successful	
12:12				Can Unsuccessiui	
12.12			C	Call Unnecessary	
Contact Attempts:			P	hone Call Occurred with:	
				▼	
Caller:  [name]					
Pre-Call Prep					
Time:	•				
Call Duration:					
1	I		I		

### **FOLLOW-UP APPOINTMENT**

[figure not shown]
**Comments:** 

Provider contacted for pain/symptoms/complications

When is your follow-up appointment?			
Follow-up appointment change made based on this call  O Yes O No			
Able to teach back follow-up appoint	ntment related to hospitalization	○ Yes ○ No	
Comments:			
MEDICATIONS:			
WEDICHTIONS.			
*Are new prescriptions identified of	n the discharge summary?		
• Yes –			
	ber] new medicines from your ho	snital visit How are you	
	ar [medication]? (follow protocol		
filled prescriptions)	a [medication]. (tonow protocor	ii you iiiu putiont nuo not	
± ± /	ugh your daily plan for taking all	your medicines	
· ·	you have about your medicines		
• No –	Š		
o I see we didn't preso	cribe any new medicines when you	u left the hospital. Is that still	
correct?			

 
Yes: Great – do you take any other medicines on a regular basis?
 
			

 
Would you talk through your daily plan for taking your medicines?
 
			
Do you have any questions about your medicines?  Not Observed medicines did you get? How are you tolerating taking your navy.			
No: Ok, what medicines did you get? How are you tolerating taking your new medicines?			

 
Would you talk through your daily plan for taking your new medicines and
 
			
any others you take on a regular basis?			
• What questions do you have about your medicines?			
O V			
Yes			
Able to teach back medications No			
	Partial Partial		
Has obtained medications	° Yes		
prescribed at discharge C No			

	O Partial	
Medication education or clarification was needed	○ Yes ○ No	
Medication change made by caller/provider based on phone call	○ Yes ○ No	
Comments:		

Meds Editor: (Click to expand/collapse)

### **CLOSING:**

- Thank you for talking with me. We are always trying to get better at giving excellent care. Is there one thing that comes to mind for you that we can improve on?
- You will be getting a survey in the mail asking about your experience during your hospital stay. We would appreciate you taking the time to give us your feedback. It is very important to us and should only take you about five minutes.
- Do you need anything from us right now?
  - Ok we wish you all the best in your recovery. If you need anything, please contact us at [phone number]

Comments:		

S ave As Draft	Complete

Form: post\_discharge\_telephone\_call (Post Discharge Telephone Call)

Version: 2.4

Last modified: \$Date: 2015/12/21 18:22:48 \$

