#### Outcome Measures

### Primary Outcome for this study is readmission within 30 days

Secondary Outcomes include evaluating: The primary outcome of readmission within 30 days within prespecified subgroups (age, gender, race, health literacy level, established primary care status, patient satisfaction, Medicare readmission penalty diagnosis status, readmission risk score), patient satisfaction between the study arms measured as mean Hospital Consumer Assessment of Healthcare Providers and Systems (HCAHPS) patient satisfaction scores, all cause VUMC ED visits, the need for assistance with discharge plan implementation, and mortality within 30 days.

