#### Study Arms

VUMC Quality Committee's Post-Hospital Discharge Program is a quality initiative started in January of 2016 where a single study nurse calls as many patients after discharge as she can reach. Using a phone call intervention script and form (See *Appendix I* – Discharge Phone Call Starform) to guide the flow of each call

and screening for discharge intervention needs. After discharge, patients will be randomized to one of 2 study arms. Enrollment projections are included in *Figure 1*.

Phone Call Group (Intervention Arm): Patients will first be called with a maximum of 3 call attempts by the study nurse made up until post-discharge day 7. The semi-structured script imbedded within the Discharge Phone Call Starform is used to guide a conversation to obtain information on potential causes of hospital readmission that can be identified and addressed to improve each patient's transition to outpatient care. We will collect data on 1) outpatient care support provided to intervention group patients exposed to the phone call intervention (coordinating the receipt of durable medical equipment, facilitating a connection with home health, referral to PCP, referral to ED, requesting the assistance of case management or social work assistance for the patient, medication change initiated by the Phone Call Nurse, requesting pharmacist assistance with discharge plan details, requesting other health providers assistance, reminding the patient of planned follow up appointments, scheduling expected follow-up appointments, providing self-care education (wound care, diet, activity), providing medication dosing and administration education), 2) whether findings from the call generate a visit to emergency department or a hospital readmission. (See Appendix I's *Starform Data* section)

Usual Care Group (Control Arm): Patients assigned to the Control Group receive standard discharge planning and follow-up per the usual care of their medical providers.

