#### Data Collection

Every weekday morning, a report will be generated from the Vanderbilt electronic medical record identifying all patients discharged from the hospital the previous day. This list will be transmitted securely to the study team. The list will then be randomized and uploaded to the study database within Research Electronic Data Capture (REDCap). This will occur using code written in R linked with the application program interface (API) function of REDCap. (See *Appendix II* – Randomization and REDCap API Database Upload Code). The code will upload patients assigned to the 2 study arms into separate database locations. The Intervention Arm Database includes a work list queue for the Study Phone Call Nurse. In addition, she will document interventions delivered via a form (*Appendix III* - Intervention Data Capture Form) for each patient's phone call encounter that will save this data as new variables within the database.

The Study Phone Call Nurse will continue to complete an existing form within the electronic health record, the Phone Call Starform (*Appendix I*) to document care provided via the phone call. For patients reached, the Study Phone Call Nurse will use the semi-structured script provided by the Starform to assess the patient's understanding of their discharge plan, screen for discharge assistance needs, and inquire about new symptoms requiring patient referral.

The majority of our study data will be obtained via Vanderbilt University Medical Center's Research Derivative. These variables include: 1) VUMC based primary outcome (hospital readmission to VUMC) data, 2) secondary outcome measures (patient satisfaction scores, all cause ED visits within 30 days, identified the need for assistance with discharge plan implementation, and 30 day mortality), 3) Hospital readmission risk score calculated for each patient before discharge which is included as part of the medical record, and 4) prespecified subgroup identifiers (see Figure 1).

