### **Appendix IV- Study Variable Summary**

#### Phone Call Study Patient Variates

BASELINE PATIENT DATA
First name
Last name
Zipcode
Medical record number
Established Primary Care Yes
No

Health Literacy BHLS Education level

Race Black White

Latino Non-white Hispanic

Multiple Races Unknown

Primary Language English

Spanish Arabic Other

Number of Hospitalizations in Prior Year

Complicating Baseline Comorbidities (Natural Language Processing)

Congestive heart failure

COPD

Readmission penalty dx - AMI, HF, PNA, COPD,

CABG, Total hip/knee repair, and stroke

Diabetes

Outpatient hospice Substance abuse Depression INDEX HOSPITALIZATION DATA

Intervention Arm Encounter Number Date of admission Time of admission

Admission day of the week Admission Diagnosis #1 Admission Diagnosis #2 Admission Diagnosis #X Highest bed level

Floor ICU Discharge Service Riven Morgan

> Geriatrics Palliative Care

Discharge Diagnosis #1 (ICD-10)
Discharge Diagnosis #2 (ICD-10)
Discharge Diagnosis #3 (ICD-10)
Discharge Diagnosis #4 (ICD-10)
Discharge Diagnosis #X (ICD-10)

Discharge Date Discharge Time

Discharge Location/Disposition

Readmission penalty dx cohort- AMI, HF, PNA, COPD, CABG, Total hip/knee repair, and stroke

Number of medications upon discharge

VUMC Cornelius Readmission Risk Score Patient satisfaction (Press Ganey Score, 1-5)

READMISSION HOSPITALIZATION DATA

Date of admission Time of admission Admission Diagnosis #1 Admission Diagnosis #2

Admission Diagnosis #X Highest bed level Floor

ICU
Discharge Diagnosis #1 (ICD-10)
Discharge Diagnosis #2 (ICD-10)
Discharge Diagnosis #3 (ICD-10)

Discharge Diagnosis #4 (ICD-10)

Discharge Diagnosis #X (ICD-10)

Readmission penalty dx - AMI, HF, PNA, COPD, CABG, Total hip/knee repair, and stroke

Discharge Date
Discharge Time
Discharge Location

Patient satisfaction (Press Ganey Score, 1-5)

Extra-Institutional Data

Survival Data (at 30 days)

Non-VUMC TN Readmission (at 30 days post VUMC

admit)

(minimum data = yes/no)

CALL INTERVENTION DATA

1st Contact

Time of first call Date of first call

Final Contact

Time of Final Contact Date of Final Contact

Call attempts

1 2 3

Not eligible AMA Facility Placement Deceased

Already seen in clinic CRC patient

Patient currently admitted/readmitted

Call status

Success

Unsuccessful - Wrong Number

Unsuccessful - Refused

Unsuccessful - Patient Call Back Requested

Unsuccessful - Patient Not Available

Unsuccessful - No Answer

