### 3. Co-Variate Distribution (*Table 1*)

- a. Patient: Age, sex, zip code, established primary care, BHLS, education level, race, primary language, VUMC admits in prior 6 mo, VUMC ED visits in prior 6 mo, PMHx (7 readmit penalty diagnoses, DM, outpatient hospice, substance abuse, depression)
- b. Index Admission: Admit diagnosis, # meds upon discharge, Cornelius score, Any ICU time, meds-to-beds program exposure, %weekend discharges, % discharges after 4pm, Hospital LOS
- 4. Outcome Analysis (ITT analysis for stat significant differences)
  - a. VUMC Readmission Rate
    - i. Rates (*Table 2* 2x2 Table)
    - ii. Descriptives for proportion readmit penalty diagnosis
  - b. Time to VUMC readmission
    - i. Kaplan-Meier Curve (Figure 2)
  - c. VUMC ED Revisit Rate
  - d. Patient Satisfaction (Press Ganey)

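### The call asks reached intervention patients to return the satisfaction survey, and the plan does not assess the differential-response bias this could cause in the between-arm satisfaction comparison

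*Combined protocol and SAP*

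**What the plan says.** - **Endpoint.** Outcome Measures lists "patient satisfaction between the study arms measured as mean Hospital Consumer Assessment of Healthcare Providers and Systems (HCAHPS) patient satisfaction scores" among the secondary outcomes.
- **Analysis.** Appendix V, item 4, puts patient satisfaction under "Outcome Analysis (ITT analysis for stat significant differences". The Study Timeline carries the same analysis to the final stage, with all satisfaction data included.
- **Survey request.** The Closing section of the Phone Call Starform (Appendix I) reads "You will be getting a survey in the mail asking about your experience during your hospital stay", followed by "We would appreciate you taking the time to give us your feedback", and stresses how much the reply matters.
- **Who hears it.** Data Collection: "For patients reached, the Study Phone Call Nurse will use the semi-structured script provided by the Starform".
- **Control arm.** Study Arms: "Patients assigned to the Control Group receive standard discharge planning and follow-up per the usual care of their medical providers". No call or survey request is described for these patients.
- **Non-response.** Neither Statistical Analysis nor Appendix V plans to report survey response by arm, compare respondents with non-respondents, or weight, impute or run a sensitivity analysis. No response rate is given anywhere.
- **Instrument.** Outcome Measures names mean HCAHPS. Appendix IV has "Patient satisfaction (Press Ganey Score, 1-5", listed for both the index and the readmission stay. Appendix V also names Press Ganey.

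**The concern.** This is more specific than ordinary survey non-response, because the randomised treatment itself contains a request to return the outcome form. Randomisation makes the arms comparable as enrolled. It does not make respondents comparable if the treatment changes who responds. Calling the analysis ITT does not help when scores exist only for those who mail back a survey.

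Suppose the request brings in patients who would otherwise not reply, and they are more or less satisfied than habitual repliers. The arm means then differ even if the call does nothing for satisfaction, and a real effect could be hidden or exaggerated in the same way. Satisfaction is part of the stated Objective and of the expected benefits in Background, so its result will be read and published. As planned, a reader could not tell an effect on satisfaction from an effect on survey return.

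**Working it through.** **1. Share of the arm that can hear the request.** Potential Risks and Benefits gives 30% reached. Sample Size Considerations projects 334 reached of 1117 called: 334/1117 = 29.9%, which agrees. (That sentence says per month, which does not fit the roughly 508 eligible patients per month in Power Calculation; only the ratio is used here.) With 1117 per arm, 0.30 × 1117 ≈ 335 intervention patients hear the request and about 782 do not.

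**2. Inputs the documents do not give (assumptions).**
- r0, base response: 15-35%, taken as equal for reached and unreached patients
- u, extra response among reached patients: 0-20 percentage points
- g, score gap between added and habitual respondents: 0-0.5 SD, either sign

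**3. Formulas**, with no true effect of the call on satisfaction:
- Share of intervention respondents added by the request: s = 0.30u / (r0 + 0.30u)
- Bias in SD units: b = s × g
- SE = √[1/(1117·r0) + 1/(1117·(r0 + 0.30u))]
- Type I error at two-sided 5%: Φ(−1.96 + b/SE) + Φ(−1.96 − b/SE)

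**4. Results at 30% reach.**

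| r0 | u | s | g | Bias (SD) | SE (SD) | Type I error |
|---|---|---|---|---|---|---|
| any | 0 | 0 | any | 0 | 0.07-0.11 | 5% |
| 25% | 10 pts | 0.03/0.28 = 0.107 | 0.2 | 0.021 | 0.082 | 5.8% |
| 25% | 10 pts | 0.107 | 0.5 | 0.054 | 0.082 | 10% |
| 15% | 20 pts | 0.06/0.21 = 0.286 | 0.5 | 0.143 | 0.101 | 29% |

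Over r0 of 15, 25 and 35%, u of 5, 10 and 20 points, and g of 0.2 and 0.5 SD (18 combinations), the bias exceeds one SE in three. All three have u = 20 points and g = 0.5 SD.

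**5. Sensitivity to arm size and reach.**
- The bias does not depend on sample size, but the SE does. The Study Summary gives 1778 per arm, which multiplies each SE by √(1117/1778) = 0.79. The middle rows become 0.065. A fourth combination (r0 15%, u 10 points, g 0.5 SD) then just reaches one SE: 0.083 against 0.083.
- Potential Risks and Benefits says that three attempts for every patient may raise delivery, without a figure. At an assumed 80% reach with r0 15%, u 20 points and g 0.5 SD, s = 0.16/0.31 = 0.516 and the bias is 0.26 SD.

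**The case against.** **Bias is not demonstrated.** A reader might infer that the comparison is biased, or that no satisfaction difference could be attributed to the call. The documents do not support that. The request must change who replies, and the added repliers must score differently; there are no data on either. In the middle case with a 0.2 SD gap the error rate moves only from 5% to 5.8%. This objection stands and sets the wording: open to bias, and not assessed.

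**Only part of the arm is exposed.** A reader might take the prompt to cover the whole intervention arm. It reaches about 30%, and the script is semi-structured, so word-for-word delivery is itself assumed. Absence of a prompt for controls is inferred from the documents' silence about what usual discharge planning contains. These points stand as limits on size.

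**Editing the script has a price.** The Starform is an existing clinical form (version 2.4, last modified December 2015) in a pragmatic trial of a running programme. Removing lines changes the programme under test. The sample record in Appendix III is dated March 2017, after accrual began on 20 February 2017, so an edit might also split the intervention into two versions. Nor would it guarantee equal response, since a personal call may itself affect survey return. This stands; the edit is optional.

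**Weighting is limited.** It corrects only selection explained by the variables in the model. If response depends on satisfaction itself, bias remains. This stands, and is why a delta adjustment is needed too.

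**Consequence is limited.** Significance and Impact ties the investment decision to the primary endpoint, which does not use the survey. That bounds the importance of the point but does not answer it, because satisfaction is still to be tested by arm.

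**Conclusion.** The point holds in limited form. The only survey request the documents describe sits inside the randomised call, mean satisfaction is compared between arms under an ITT label, and nothing in the plan examines who responded. The comparison is therefore open to differential-response bias of unknown size and direction.

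On the assumed ranges at 30% reach, the bias is 0 to 0.14 SD against standard errors of 0.07 to 0.11 SD (1117 per arm). It is usually below one standard error and exceeds it when uplift and score gap are both large. Only the 30% reach and the arm size come from the plan; base response, uplift and gap are assumptions.

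It would be wrong to extend the point to the primary outcome: the between-arm readmission comparison does not depend on survey return. The difference in instrument names is a separate inconsistency unrelated to the script, but it affects the same endpoint and should be settled at the same time.

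**What to change.** In Statistical Analysis and Appendix V, item 4:

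1. Report survey response by arm and, within the intervention arm, by reached or not reached.
2. Compare respondents' baseline characteristics between arms.
3. Alongside the comparison of mean scores, add an analysis weighting respondents by the inverse of their estimated probability of response, using baseline variables already listed in Appendices IV and V (for example age, sex, race, health literacy, education, language, primary care status, prior admissions, readmission risk score).
4. Add a delta-adjusted sensitivity analysis in which non-respondents' scores are shifted by a range of amounts, separately by arm, and report the shift at which the conclusion would change.
5. State that the satisfaction result is a comparison among respondents.
6. Name one instrument and score, and use it consistently in Outcome Measures, Appendix IV and Appendix V.

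The cost is a little more analysis work and a more cautious satisfaction conclusion. All six steps can be done without touching the intervention, even after enrolment has closed, provided they are fixed before satisfaction is compared by arm. Dropping the survey lines from study calls is an option for the sponsor to weigh: it removes the described prompt but alters the programme form under test.
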